5.5.5 Exploratory or Correlative Analyses

Additional PK or PD analyses may be performed, as deemed appropriate.

Correlations between subject characteristics and outcome measures and correlations among outcomes measures will be explored using regression models or other appropriate techniques. Such evaluations may assist in determining if baseline parameters or early changes in PD biomarkers are predictive of response to Btk inhibition.

6.0 ASSESSMENT OF SAFETY

Safety assessments will consist of monitoring and recording AEs and SAEs; measurements of protocol-specified hematology, clinical chemistry, urinalysis, and other laboratory variables; measurement of protocol-specified vital signs; and other protocolspecified tests that are deemed critical to the safety evaluation of the study drug(s).

6.1 **DEFINITIONS**

6.1.1 Adverse Events

An AE is any unfavorable and unintended sign, symptom, or disease temporally associated with the use of an investigational (medicinal) product or other protocolimposed intervention, regardless of attribution.

This includes the following:

- AEs not previously observed in the subject that emerge during the protocol-specified AE reporting period, including signs or symptoms associated with MM that were not present before the AE reporting period (see Section 6.2.1)
- Complications that occur as a result of protocol-mandated interventions (eg, invasive procedures such as biopsies)
- Preexisting medical conditions (other than the condition being studied) judged by the investigator to have worsened in severity or frequency or changed in character during the protocol-specified AE reporting period.

Abnormal laboratory values should not be reported as AEs; however, any clinically significant laboratory values (defined as requiring treatment, discontinuation from study, or dose modification) should be reported as AEs.

6.1.2 Serious Adverse Event

The terms "severe" and "serious" are not synonymous. Severity (or intensity) refers to the grade of an AE (see below). "Serious" is a regulatory definition and is based on subject or event outcome or action criteria usually associated with events that pose a threat to a subject's life or functioning. Seriousness (not severity) serves as the guide for defining regulatory reporting obligations from the Sponsor to applicable regulatory authorities.

An AE should be classified as an SAE if it meets any 1 of the following criteria:

• It results in death (ie, the AE actually causes or leads to death).

- It is life-threatening (ie, the AE, in the view of the investigator, places the subject at immediate risk of death. It does not include an AE that, had it occurred in a more severe form, might have caused death).
- It requires or prolongs in-patient hospitalization.
- It results in persistent or significant disability/incapacity (ie, the AE results in substantial disruption of the subject's ability to conduct normal life functions).
- It results in a congenital anomaly/birth defect in a neonate/infant born to a mother exposed to the investigational product.
- It is considered a significant medical event by the investigator based on medical judgment (eg, may jeopardize the subject or may require medical/surgical intervention to prevent 1 of the outcomes listed above).

6.1.3 Severity

Definitions found in the CTCAE version 4.03 or higher will be used for grading the severity (intensity) of AEs. The CTCAE displays Grades 1 through 5 with unique clinical descriptions of severity for each referenced AE. Should a subject experience any AE not listed in the CTCAE, the following grading system should be used to assess severity:

- Grade 1 (Mild AE) experiences which are usually transient, requiring no special treatment, and not interfering with the subject's daily activities
- Grade 2 (Moderate AE) experiences which introduce some level of inconvenience or concern to the subject, and which may interfere with daily activities, but are usually ameliorated by simple therapeutic measures
- Grade 3 (Severe AE) experiences which are unacceptable or intolerable, significantly interrupt the subject's usual daily activity, and require systemic drug therapy or other treatment
- Grade 4 (Life-threatening or disabling AE) experiences which cause the subject to be in imminent danger of death
- Grade 5 (Death related to AE) experiences which result in subject death

6.2 DOCUMENTING AND REPORTING OF ADVERSE AND SERIOUS ADVERSE EVENTS

The investigator is responsible for ensuring that all AEs and SAEs that are observed or reported during the study, as outlined in the prior sections, are recorded on the eCRF. All SAEs also must be reported on the SAE/Product Complaint form (see Section 6.2.4).

6.2.1 Adverse Event Reporting Period

The AE reporting period for this study begins when the subject receives the first dose of study medication and ends with the safety follow-up visit (or last on-treatment visit if the safety follow-up visit is not done), or when the subject receives a new anticancer therapy. An exception to this reporting period is any AE occurring due to a protocol-defined screening procedure. Fatal AEs occurring within 30 days after the last dose of ACP-196 *AND* assessed by the investigator as related to ACP-196 must be reported as a SAEs.

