Subjects who discontinue study therapy will continue on study for safety (Section 4.3) unless they withdraw consent for further follow-up. Thus, all subjects receiving \geq 1 dose of study drug will be followed during the immediate posttherapy period unless the subject withdraws consent for such follow-up to be conducted. The date the subject is withdrawn from study treatment or from the study and the reason for discontinuation will be recorded and also should be described on the appropriate eCRF.

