4.3 EARLY TERMINATION/SAFETY FOLLOW-UP VISIT

An early termination visit is required for any subjects who permanently discontinue study drug early for any reason including disease progression. Each subject should be followed for 30 (±7) days after his or her last dose of study drug (ie, the "safety follow-up visit") to monitor for resolution or progression of AEs (see Section 6.2.5) and to document the occurrence of any new events; unless, the subject receives a new anticancer therapy within this timeframe. Subjects who withdraw consent should still be encouraged to complete the safety follow-up assessments, but these assessments cannot be mandated once consent is withdrawn. The Schedule of Assessments (Appendix 5) describes the procedures required for the safety follow-up.

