### 10.6 Analyses of Safety Endpoints

Safety analyses will be performed on All-treated population by treatment cohort.

Analyses of adverse events (AEs) will be performed on treatment-emergent AE (TEAE) data, unless otherwise specified. TEAEs are defined as those events with onset or

worsen date on or after the date of first dose of acalabrutinib, through the treatment phase to last dose of acalabrutinib, and within 30 days following the last dose of acalabrutinib, whichever is later. Common Terminology Criteria for Adverse Events (CTCAE) Version 4.03 or higher is used for AE grading.

Treatment-emergent AEs will be summarized in 3 groups: (1) acalabrutinib monotherapy, (2) acalabrutinib + dexamethasone, and (3) crossover from monotherapy to acalabrutinib + dexamethasone therapy. By this grouping method, AEs among subjects assigned to acalabrutinib monotherapy will be reported in group 1 when AEs occurred before crossover, and AEs occurred on/after crossover will be reported in group 3. Treatment-emergent AEs occurred on or after crossover will be summarized in the crossover group. Treatment-emergent AEs occurred before crossover will be summarized in the monotherapy group. All AE terms will be coded by Medical Dictionary for Regulatory Activities (MedDRA) Version 19.1 and will be presented by system organ class (SOC) and preferred term (PT). Treatment-emergent AEs will be summarized by SOC and PT and by CTCAE toxicity grade. The drug-related AEs, serious adverse events (SAEs) and drug-related SAEs, AEs leading to treatment discontinuation, dose delay and dose modification will be summarized by PT by CTCAE toxicity grade.

Death will be reported in a listing and summarized. A table will be provided for grade 5 AE and the relationship with any study drug.

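### Protocol 6.2.1 closes AE reporting at the last on-treatment visit when the follow-up visit is missed, short of the SAP's 30-day window, and its fatal-AE sentence covers only events related to ACP-196

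*Protocol*

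**What the plan says.** Protocol 6.2.1 opens the AE reporting period at the first dose. The period "ends with the safety follow-up visit (or last on-treatment visit if the safety follow-up visit is not done", and it also closes when a new anticancer therapy is received. The section has one sentence on deaths. It concerns "Fatal AEs occurring within 30 days after the last dose of ACP-196", and its second condition, with the duty attached, reads "assessed by the investigator as related to ACP-196 must be reported as a SAEs". Dexamethasone is not named.

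Other parts of the plan bear on the same events:

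- Protocol 6.1.2 makes an AE serious if "It results in death (ie, the AE actually causes or leads to death", with no reference to cause.
- Protocol 6.2 asks for every AE and SAE observed or reported during the study to be recorded. Section 6.2.4 asks for every SAE within 24 hours and for each death to be reported under its primary cause. Neither sets a causality condition.
- Protocol 6.2.5 follows AEs to resolution, but only those that arise inside the reporting period.
- Protocol 3.8 says that every dosed subject "will be followed during the immediate posttherapy period unless the subject withdraws consent". Section 4.3 adds "Each subject should be followed for 30 (±7) days after his or her last dose of study drug", except where a new anticancer therapy starts first, and "An early termination visit is required for any subjects who permanently discontinue study drug early for any reason including disease progression".
- SAP 10.6 counts treatment-emergent AEs from the first acalabrutinib dose to 30 days after the last, without reference to any visit. It plans a listing and summary of deaths, and then: "A table will be provided for grade 5 AE and the relationship with any study drug".

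**The concern.** Characterising safety is the primary objective (Protocol 2.1). Under 6.2.1 the end of collection is known only afterwards, because it depends on whether a later visit took place. A subject who dies before that visit cannot attend it, so the event can itself move the closing date back to before the event began. The fatal-AE sentence restores some of these events, but only those attributed to ACP-196.

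The analysis makes no such distinction. SAP 10.6 sets a fixed 30-day window for everyone and tabulates grade 5 AEs by relationship to any study drug. If sites apply 6.2.1 literally, collection stops before the analysis window does, and the sentence on deaths protects one causality category only. If they apply 6.2.4, it does not. Capture could then differ by site in a trial planned for about 20 sites (Protocol 3.1).

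**Working it through.** The plan gives no figure to reproduce. The check is a comparison of rules, followed by the length of the gap.

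**1. One case under each rule.** Suppose a subject is last seen at Cycle 4 Day 28, keeps dosing, and dies 21 days later of an event that began after that visit. No follow-up visit takes place.

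| Source | Event judged related to ACP-196 | Event judged unrelated, or related to dexamethasone only |
|---|---|---|
| Protocol 6.2.1 alone | Reported as an SAE through the fatal-AE sentence | Outside the period, which closed 21 days before death |
| Protocol 6.1.2, 6.2, 6.2.4 | SAE, reportable | SAE, reportable |
| SAP 10.6, TEAE and grade 5 table | Counted | Counted, if it was collected |
| SAP 10.6, death listing; SAP 14.3, PFS | Death appears | Death appears |

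The conflict lies in the right-hand column of the first row. A non-fatal AE with onset after the last on-treatment visit is outside 6.2.1 in the same way, whatever its cause.

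**2. An event that began earlier.** If the AE started before the last on-treatment visit, 6.2.5 follows it to its outcome, so a fatal outcome is captured whatever its cause. Only onset after that visit is exposed.

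**3. A visit waived for new therapy.** Sections 3.1 and 4.3 waive the follow-up visit when a new anticancer therapy starts within the follow-up time. Section 6.2.1 then offers two closing dates, the last on-treatment visit and the start of the new therapy, and does not say which governs.

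**4. Length of the uncovered span.** Inputs: visits on a 28-day cycle from Cycle 3, with a ±2-day window (Protocol 3.1 and Appendix 5); follow-up visit at 30 (±7) days (Protocol 4.3); TEAE window of 30 days after the last dose (SAP 10.6).

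Span = (last dose − last on-treatment visit) + days after the last dose.

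- Early termination visit at about the last dose, counted as the last on-treatment visit (assumption): 0 + 30 = 30 days. Measured to the latest permitted follow-up visit, 30 + 7 = 37 days.
- No early termination visit, and the last dose just before the next visit was due: 28 + 30 = 58 days. If both visit windows widen the interval, 28 + 2 + 2 + 30 = 62 days.
- Death while still dosing: the span ends at death, so it is at most about 28 days, or 28 + 2 + 2 = 32 with the windows.

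On days 31 to 37 the fatal-AE sentence has lapsed too, so on 6.2.1 alone even a related fatal AE with onset then is not covered. Those days are also beyond the SAP's TEAE window.

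**The case against.** The strongest answer is that the protocol does not rest on 6.2.1 alone. Sections 6.2 and 6.2.4, and the investigator duties in 7.12, ask for all SAEs, and 6.2.4 for all deaths, with no causality or visit condition. Section 6.2.2 accepts events found by means other than a visit. The fatal-AE sentence says what must be reported and never says that other fatal AEs need not be. It can be read as an addition, for example where new therapy has already closed the period. Sections 3.8 and 4.3 intend every dosed subject to be followed after therapy, and the early termination visit is mandatory. Deaths enter the SAP's listing and the PFS analysis whatever their cause.

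All of this stands, and it limits the point. A reader might infer from 6.2.1 that a fatal AE is reportable only if related to ACP-196. The documents taken together do not support that. A reader might also infer that deaths would be lost, and the death listing rules that out.

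The answer does not remove the conflict. Section 6.2.1 is where the period is defined, and other sections lean on it: 6.1.1 describes new AEs as those arising within that period, and 6.2.5 confines follow-up to it. A site could follow 6.2.1 or 6.2.4 in good faith and enter different data. For non-serious AEs after the last on-treatment visit, only the general wording of 6.2 and 6.2.2 points the other way.

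**Conclusion.** The point holds as a conflict between Protocol 6.2.1 and Protocol 6.1.2, 6.2 and 6.2.4, and between 6.2.1 and SAP 10.6. When the follow-up visit is missed, the stated collection period can end before the analysis window. What is at risk is incomplete and site-dependent capture of late AEs, and of grade 5 AEs judged unrelated or related to dexamethasone only.

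The uncovered span is about 30 days if an early termination visit at the last dose is done and counted as on-treatment, which 6.2.1 does not state. It is up to about 58 days if that visit is also missed. These are lengths of time, not numbers of events. The documents do not say how many subjects miss the visit, so no loss can be estimated.

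Two further inferences go beyond the documents. One is that visits are missed mainly because subjects have died or are in hospital. The only reason the plan gives for omitting the visit is new anticancer therapy. The other is that the grade 5 table will understate fatal events and inflate the related share. That is the direction to expect if sites follow 6.2.1 literally, but nothing shows that they would. One event would be 1/20 = 5 percentage points of a planned cohort, which gives the scale only. SAP 3.1 records that enrolment was stopped early, so 20 is the planned number and not necessarily the number enrolled.

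**What to change.** In Protocol 6.2.1:

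- Delete the parenthesis on the last on-treatment visit. End the period 30 days after the last dose of study drug, or at the safety follow-up visit if that is later, or at the start of a new anticancer therapy, whether or not the visit takes place.
- Reword the fatal-AE sentence so that every fatal AE within 30 days after the last dose is reported as an SAE regardless of relationship, in line with 6.1.2, 6.2.4 and SAP 10.6.
- Where the visit is missed and consent stands, ascertain AEs by telephone or from records.

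The protocol already uses a date 30 days after the last dose for concomitant medications (4.1.4) and pregnancies (6.2.3). SAP 10.6 counts from the last acalabrutinib dose and has no cut at new anticancer therapy. One sentence there should say how AEs after new therapy are treated, and how the window is set if dexamethasone outlasts acalabrutinib.

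The cost is a change of wording, CRF guidance, and a telephone or record check for the few subjects who miss the visit. No visits are added. For subjects already past this point, the report can state how many had no follow-up visit and reconcile the death listing with the grade 5 table.

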6.2.2 Assessment of Adverse Events

Investigators will assess the occurrence of AEs and SAEs at all subject evaluation time points during the study. All AEs and SAEs whether volunteered by the subject, discovered by study personnel during questioning, or detected through physical examination, or other means will be recorded in the subject's medical record and on the AE eCRF and, when applicable, on an SAE/Product Complaint form.

Disease progression itself is not considered an adverse event; however, signs and symptoms of disease progression may be recorded as AEs or SAEs.

Each recorded AE or SAE will be described by its duration (ie, start and end dates), severity, regulatory seriousness criteria, if applicable, suspected relationship to the study drug (ie, ACP-196, dexamethasone, or both; see following guidance), and any actions taken. The relationship of AEs to the study drug will be assessed by means of the question: 'Is there a reasonable possibility that the event may have been caused by the study drug?' Answer Yes or No.

See Appendix 2 for more detail on assessing relationship.

6.2.3 Pregnancy

The investigator should report all pregnancies in study subjects and in the partners of subjects within 24 hours using the Pregnancy Report Form. This form should be faxed or emailed to Acerta Pharma Drug Safety. Any pregnancy-associated SAE must be

reported using the SAE report form, according to the usual timelines and directions for SAE reporting (Section 6.2.4).

Any uncomplicated pregnancy that occurs in a subject or a partner of a treated subject during this study will be reported for tracking purposes only, if agreed to by the subject or the partner of the subject in this study. All pregnancies and partner pregnancies that are identified during or after this study, wherein the estimated date of conception is determined to have occurred from the time of consent to 30 days after the last dose of study medication will be reported, followed to conclusion, and the outcome reported, as long as the subject or partner is willing to participate in follow-up.

Pregnancy itself is not regarded as an AE unless there is suspicion that the investigational product under study may have interfered with the effectiveness of a contraceptive medication. Likewise, elective abortions without complications are not considered AEs. Any SAEs associated with pregnancy (eg, congenital abnormalities/birth defects/spontaneous miscarriages or any other serious events) must additionally be reported as such using the SAE/Product Complaint form.

Subjects should be instructed to immediately notify the investigator of any pregnancies. Any female subjects receiving ACP-196 who become pregnant must immediately discontinue study drug. The investigator should counsel the subject, discussing any risks of continuing the pregnancy and any possible effects on the fetus.

6.2.4 Expedited Reporting Requirements for Serious Adverse Events

All SAEs must be reported within 24 hours of discover. All initial SAE reports and followup information will be reported using the protocol-specific electronic data capture system. If electronic SAE reporting is not available, paper SAE/Product Complaint forms must be emailed or faxed to Acerta Pharma Drug Safety, or designee. Acerta Pharma may request follow-up and other additional information from the investigator (eg, hospital admission/discharge notes and laboratory results).

All deaths should be reported with the primary cause of death as the AE term, as death is typically the outcome of the event, not the event itself. The primary cause of death on the autopsy report should be the term reported. Autopsy and postmortem reports must be forwarded to Acerta Pharma Drug Safety, or designee, as outlined above.

If study drug is discontinued because of an SAE, this information must be included in the SAE report.

An SAE may qualify for mandatory expedited reporting to regulatory authorities if the SAE is attributable to the investigational product and is not listed in the current Investigator's Brochure (ie, an unexpected event). In this case, Acerta Pharma Drug Safety/Designee will forward a formal notification describing the SAE to all investigators. Each investigator must then notify his or her IRB/IEC of the SAE.

6.2.5 Type and Duration of Follow-up of Subjects After Adverse Events

All AEs and SAEs that are encountered during the protocol-specified AE reporting period should be followed to resolution, or until the investigator assesses the event as stable, a new anticancer therapy is initiated, or the subject is lost to follow-up or withdraws consent.

7.0 STUDY ADMINISTRATION AND INVESTIGATOR OBLIGATIONS

Acerta Pharma retains the right to terminate the study and remove all study materials from a study site at any time. Specific circumstances that may precipitate such termination include:

- Unsatisfactory subject enrollment with regard to quality or quantity
- Significant or numerous deviations from study protocol requirements, such as failure to perform required evaluations on subjects and maintain adequate study records
- Inaccurate, incomplete or late data recording on a recurrent basis
- The incidence and/or severity of AEs in this or other studies indicating a potential health hazard caused by the study treatment

7.1 REGULATORY AND ETHICAL COMPLIANCE

This clinical study was designed and will be implemented in accordance with the protocol, the ICH Harmonized Tripartite Guidelines for Good Clinical Practices, applicable local regulations (including US Code of Federal Regulations Title 21 and

European Directive 2001/20/EC), and the ethical principles laid down in the Declaration of Helsinki.

7.2 INSTITUTIONAL REVIEW BOARD AND INDEPENDENT ETHICS COMMITTEE

The investigator will submit this protocol, the ICF, Investigator's Brochure, and any other relevant supporting information (eg, all advertising materials) to the appropriate IRB/IEC for review and approval before study initiation. A signed protocol approval page; a letter confirming IRB/IEC approval of the protocol and informed consent; and a statement that the IRB/IEC is organized and operates according to GCP and the applicable laws and regulations; **must** be forwarded to Acerta Pharma **before** screening subjects for the study. Additionally, sites must forward a signed FDA 1572 form (Statement of Investigator form) to Acerta Pharma before screening subjects for study enrollment. Amendments to the protocol must also be approved by the IRB/IEC and local regulatory agencies, as appropriate, before the implementation of changes in this study.

